
The baseline assessment will take approximately 2.5 hours and will consist of a 45-60 minute structured clinical interview (SCID) using DSM-4 criteria to establish psychiatric diagnoses, depression, quality of life, and other assessments (see Table 2 for a complete list), as well as information about number of asthma-related hospitalizations, ER visits, and unscheduled clinic appointments by the child within the preceding 12 months as assessed by caregiver report (and confirmed through medical records when possible). Caregivers not meeting criteria for the intervention study will be paid for the initial assessment, informed of any psychiatric disorders identified (e.g. a psychiatric disorder other than MDD) and, when appropriate, given referral information. Caregivers with current MDD and meeting all inclusion criteria will be offered algorithm-based depression pharmacotherapy for 52 weeks. If a caregiver does not elect to participate in the algorithm-based treatment, they will remain eligible to enroll in the study and will receive referral information for an alternative depression treatment (e.g., psychotherapy) from a study psychiatrist. The caregiver will be still eligible to enroll in pharmacotherapy during a later stage of the study and will be advised by a study psychiatrist if they elect this option. Furthermore, participants who are currently receiving or plan to receive treatment for depression (e.g. medication, psychotherapy) by a healthcare provider outside of the study may also participate. In these cases the participants will receive all of the assessments and physician evaluation but will not receive algorithm-based treatment as part of the study. This protocol modification should improve enrollment by allow potential participants who prefer psychotherapy or want to receive antidepressant care from their PCPs to enroll. Given the inclusion, exclusion and discontinuation criteria, as well as the careful monitoring during the study this change should not adversely impact the safety profile of the study. The change is scientifically sound because the aims of the study are related to relationships between depressive symptom changes in the caregiver and asthma control in the child regardless of the method by which the changes were achieved. A total of 196 caregivers will be enrolled. A modified and simplified version the Texas Medication Algorithm Project (TMAP) MDD guidelines (Appendix 2) will be utilized to guide treatment. Caregivers and children will be assessed every four weeks (weeks 4, 8, 12, 16, 20, 24, 28, 32, 36, 40, 44, 48 and 52) with additional phone assessments 2 weeks after medication changes to assess for adverse events, medication side effects, or suicidality, and to confirm the next clinical appointment. Follow-up assessments will take approximately 1.5 hours including psychiatrist assessment and quality of life, asthma adherence, anxiety and depression questionnaires administered by a research team member. Caregivers will be assessed by a study psychiatrist at appointments for medication management. Caregivers will be paid \$60 for the baseline visit and assessments every 4 weeks (weeks 4-52). Children will be paid \$20 at each visit. Bus, rail, or taxi expenses will be reimbursed if these transportation methods are needed. Both caregivers and children will be paid using a UT Southwestern issued

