3.3.d.i. Psychiatric diagnoses: The SCID for DSM-4 Clinician Version (SCID-CV) is a fairly brief version of the SCID that assesses Axis I disorders in DSM-4 including MDD, dysthymic disorder, bipolar disorders, schizophrenia, anxiety disorders, eating disorders, and drug/alcohol abuse/dependence. **3.3.d.ii. Depression and anxiety measures:** A 2-item self-report screening tool for depression (2-SRSD) taken from the Primary Care Evaluation of Mental Disorders Procedure (PRIME-MD) screening interview will be used to detect suspected cases of depression among asthma clinic caregivers.⁵⁵ This instrument had better sensitivity (96%) than either the Center for Epidemiologic Studies Depression Scale (CES-D) (93%) or BDI (89%) in identifying depression as defined by structured clinical interview in a general medical clinic.⁵⁵ Specificity of the 2-SRSD was 57%. A positive answer to either 1) “During the past month, have you often been bothered by feeling down, depressed, or hopeless?” or 2) “During the past month, have you often been bothered by little interest or pleasure in doing things?” will be considered a possible case of depression and qualify for further assessment. [name] has used this screening tool in prior studies including an ongoing NHLBI-funded study in adults with asthma. The HRSD (17-item version)⁴⁷ is an observer-rated measure of depressive symptomatology. The HRSD will be given at every visit. Because of its wide use for many decades, the HRSD will be the primary measure of caregiver depressive symptoms in the study. The QIDS-SR⁴⁸ is a validated 16-item self-report scale that assesses depressive symptom severity. Scores of ≤ 7 are considered normal, 8-12 suggest mild depressive symptoms, 13-16 moderate depressive symptoms, 17-20 moderate to severe depressive symptoms, and ≥ 21 severe depression. The use of these two depression instruments allows us to assess changes in both clinician-rated and self-reported depressive symptoms and their relationship to asthma outcomes. Perceived Stress Scale (PSS) is a 10 question self-report measure validated in middle school children and adults, and available in both English and Spanish. This instrument will be administered to the caregiver and the child at each visit, and will allow for detection of changes in stress levels that are not as severe as depression and anxiety. Research coordinators will assist younger children, if necessary, by helping them read and understand the questions. The Relatedness Questionnaire is a validated 17-item questionnaire completed by the child regarding his or her primary caregiver. It will assess the quality of the child’s self-reported relationship with the caregiver.⁵⁷ Screen for Child Anxiety Related Disorders (SCARED) is a 41-item self-report scale, validated in

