Aim 2. Determine if improvement in depressive symptoms in caregivers of children with asthma predicts reduced unscheduled asthma-related service utilization. Separate analyses will be done for each event (ER visits, hospitalizations and unscheduled appointments). The dependent variable will be a count of the number of times the event occurred during the 52 week study period. This number will be converted to events per month to adjust for subjects who do not complete 52 weeks. The independent variables will be caregiver depressive symptoms as measured by HRSD along with site, baseline depressive symptoms, baseline asthma symptoms, and season of the year. Other baseline demographic and clinical variables (such as child's age) will be added if they improve the fit of the final model. Because the dependent variable is accumulated over the study period, caregiver HRSD will also be summarized over the study period for each subject by computing a seasonally adjusted slope of change over time during the 52 week study. All participants with two or more post-baseline HRSD measurements will be included in the analyses. Count data typically follow a Poisson distribution. Therefore, a generalized linear mixed model with Poisson link function will be used (SAS Proc GLIMMIX). Intercepts will be random effects. If an excessive number of subjects have zero events and the Poisson distribution is not appropriate (which often occurs with count data), then we will consider negative binomial models, zero-inflated Poisson models, and hurdle models. At times caregiver depression may get worse, despite treatment. Therefore, we will examine whether increases in caregiver depressive symptom severity predicts worse child asthma outcomes. The same model used above will be used here except that an indicator variable will be added to indicate if caregiver HRSD scores worsened or stayed the same during the study (zero or positive slope) versus improved (negative slope). The addition of this indicator variable will allow the relationship between change in HRSD and utilization events to differ for those who worsen or stay the same versus those who improve. This aim will be tested by the significance of this additional indicator variable. The primary analysis for this aim will use HRSD scores and ER visits (sensitive to the intervention in Pilot Study #2 and an important clinical outcome). However, similar analysis will be conducted using the QIDS-SR and STAI in place of the HRSD, and using unscheduled clinic visits and hospitalizations.

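### Aim 2 uses a per-caregiver HRSD slope that as few as two post-baseline scores can supply, with no stated allowance for unequal slope precision

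*Combined protocol and SAP*

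**What the plan says.** Section 3.4, Aim 2, reduces each caregiver's HRSD course to one number by "computing a seasonally adjusted slope of change over time during the 52 week study". The entry rule is "All participants with two or more post-baseline HRSD measurements will be included in the analyses". The slope is the exposure in a Poisson mixed model with random intercepts, and its sign separates caregivers who improved from those who worsened or stayed the same.

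For the outcome, "This number will be converted to events per month to adjust for subjects who do not complete 52 weeks"; no person-time offset or weight is mentioned. The covariates include "baseline asthma symptoms, and season of the year", and it is not said which season applies to a total accumulated over a year.

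On data density, section 3.3.c states that "Caregivers and children will be assessed every four weeks" (weeks 4 to 52), and section 3.3.d.ii that "The HRSD will be given at every visit". A complete record therefore has 14 scores including baseline.

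The plan does not say whether the slope comes from the caregiver's own scores or from a pooled model, whether baseline enters it, or how season is removed. The Missing Data paragraph adds a dropout indicator. That addresses non-random dropout, not slope precision.

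**The concern.** The precision of a fitted slope depends mainly on how long the scores span. A caregiver seen for eight weeks and one seen for a year would each contribute one slope to the same regression. If nothing accounts for the difference, the imprecise slopes act as high-leverage points and pull the HRSD coefficient toward zero. The split by sign inherits the same error. A real link between caregiver improvement and fewer ER visits, the primary analysis of this aim, could then be underestimated or missed.

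**Working it through.** **The plan's own figure.** The Power paragraph gives a detectable f² of 0.10 for N = 175, 10 predictors and 80% power. With a noncentral F test (u = 10, v = 164, λ = f² × N, alpha assumed 0.05) the result is f² = 0.098, so it reproduces, as a joint test of all ten predictors. It makes no allowance for error in the exposure.

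**Slope precision.** Suppose each slope is a least-squares fit to the caregiver's own scores. Its error variance is σ² / Sxx, where Sxx is the sum of squared deviations of visit weeks from their mean. On the 52-week-change scale the SE is 52σ / √Sxx.

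| Weeks with scores | Sxx | Variance relative to full | SE in units of σ |
|---|---|---|---|
| 0, 4, ..., 52 (14 scores) | 3640 | 1 | 0.86 |
| 0, 4, ..., 24 (7 scores) | 448 | 8.1 | 2.46 |
| 0, 4, 8 | 32 | 114 | 9.19 |
| 0, 4, 52 | 1675 | 2.2 | 1.27 |
| 0, 24, 52 | 1355 | 2.7 | 1.41 |

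The ratios need no assumption about σ. The last three rows each have two post-baseline scores; the damage comes from short follow-up, not from the count of scores. With σ assumed to be 4 HRSD points (range 3 to 5), the SE is 3.4 (2.6 to 4.3) with full follow-up and 37 (28 to 46) for weeks 0, 4 and 8.

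**Attenuation of the coefficient.** Attenuation = V / (V + E), where V is the variance of true 52-week change and E is the mean of 52²σ² / Sxx over caregivers. This is the linear, equal-weight approximation. Assume a true-change SD of 8 (V = 64) and σ = 4.

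- All complete: E = 2704 × 16 / 3640 = 11.9; 64 / 75.9 = 0.84.
- Cited retention (section 3.3.c.ii: 100%, 99.5%, 83.2% and 75.9% at 3, 6, 9 and 12 months): 0.5%, 16.3% and 7.3% leave in the successive quarters. With last visits placed at weeks 16, 28 and 44, the error variances are 270.4, 64.4 and 18.9. E = 0.005 × 270.4 + 0.163 × 64.4 + 0.073 × 18.9 + 0.759 × 11.9 = 22.2; 64 / 86.2 = 0.74. Last visits at weeks 12, 24 and 36 give 0.68; at weeks 24, 36 and 48, 0.80. About 0.75 is a fair summary.
- If 2% stop at week 8 (error variance 2704 × 16 / 32 = 1352): E = 0.98 × 22.2 + 0.02 × 1352 = 48.8; 64 / 112.8 = 0.57. These 2% supply 27.0 / 48.8 = 55% of the error variance.
- If 5% stop at week 8: E = 0.95 × 22.2 + 0.05 × 1352 = 88.7; 64 / 152.7 = 0.42.

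At the cited retention, a true-change SD of 6 with σ = 5 gives 36 / (36 + 34.8) = 0.51, and an SD of 10 with σ = 3 gives 100 / (100 + 12.5) = 0.89.

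**Season.** An intercept, a slope and one season contrast use up three scores and leave no residual degrees of freedom. If all three visits fall in one season, the contrast cannot be estimated. For such caregivers the adjustment must come from a pooled model.

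**Simulation under the same SDs** (196 caregivers, 800 runs, Poisson ER visits at the pilot exit rate of 0.16 per month, assumed log rate ratio 0.14 per SD of true slope). Entries are the share of the true coefficient recovered / power.

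| Stopping at two post-baseline visits | Own slope, unweighted monthly rate | Own slope, offset | Mixed-model slope, offset |
|---|---|---|---|
| None (cited retention) | 0.73 / 56% | 0.77 / 61% | 0.98 / 61% |
| 2% | 0.58 / 41% | 0.74 / 62% | 1.02 / 64% |
| 5% | 0.44 / 25% | 0.69 / 57% | 1.03 / 62% |
| 10.7% | 0.29 / 18% | 0.58 / 46% | 0.99 / 59% |

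The 10.7% row is the whole enrolment allowance, (196 − 175) / 196, taken as week-8 leavers. The sign of the slope was wrong for about 42% of two-visit caregivers, against 12% of all caregivers at the cited retention.

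**The case against.** The plan nowhere says that slopes are fitted one caregiver at a time or entered as equally precise. Mixed-model predictions also give one slope per subject, and since season cannot be removed from three scores alone, some pooling is implied. This stands: a reader might infer that the plan treats all slopes alike, but that is an inference from silence. It does not clear the plan, because pooling the season terms does not by itself shrink the slopes.

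A reader might also infer that short follow-up swamps the exposure in this trial. The documents do not support that. On the cited retention nobody has left by month 3, and the coefficient moves only from about 0.84 to about 0.75. The severe cases need about 2% or more of caregivers to stop at two post-baseline visits. Section 3.3.c.ii allows for some early attrition but gives no timing, and the cited retention comes from another study.

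Nor does the 10.7-fold SE apply to everyone with two post-baseline scores. Participants stay in the study despite missed visits, and scores at weeks 0, 4 and 52 give about 1.5 times the full-follow-up SE. The 37-point SE should not be set against the pilot's 6-month HRSD fall of 20.9 − 15.5 = 5.4; on a linear annual scale that fall is 10.8.

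Much of the simulated loss comes from the unweighted monthly rate. An offset alone lifts recovery from 0.44 to 0.69 at 5%. At the cited retention the full repair raises power only from 56% to 61%; the gain there is mainly in bias.

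Finally, it is tempting to say that the season covariate cannot adjust anything in completers. That holds only if it means the seasons covered. Season of entry would vary among completers, so the covariate is undefined rather than useless.

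**Conclusion.** The point holds in bounded form. Aim 2 makes a per-subject slope and its sign the exposure, lets two post-baseline scores suffice, and states nothing to handle unequal precision. If slopes come from own scores, the variance ratios of 114 (weeks 0, 4 and 8) and 8 (leaving at week 24) follow from the visit schedule alone, given independent errors of equal variance.

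The bias rests on assumptions. With a true-change SD of 8 and a residual SD of 4, attenuation is about 0.84 if all complete, about 0.75 at the cited retention (roughly 0.5 to 0.9 over change SD 6 to 10 and residual SD 3 to 5), and 0.57 or 0.42 if 2% or 5% stop at two post-baseline visits. The documents give neither SD nor that share. If the sponsor already intends shrunken slopes from a pooled model, naming the estimator resolves most of the point. As written, the plan should be changed before analysis.

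**What to change.** 1. Fit one linear mixed model to all HRSD scores, with a random intercept and slope per caregiver and calendar-season terms shared by everyone. Use its predicted slopes as the Aim 2 exposure, or fit a joint model of HRSD and event counts. State that baseline is included.
2. Model the event counts with a log person-time offset in place of unweighted events per month.
3. Define the season covariate, for example as season of entry, or use season of the interval in an interval-level count model.
4. Add a sensitivity analysis with a longer minimum follow-up.

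The cost is SAP wording and one extra model; no new data are needed. There is one downside. Shrinkage moves the slopes of short-follow-up caregivers toward the mean, so if caregivers improve on average most of them would be classed as improved. The improved/worsened indicator should therefore be interpreted with caution or limited to caregivers with adequate follow-up, defined in advance.

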Buffalo: The Buffalo pediatric asthma service ([name], co-I) that will be used for enrollment is a three-site practice with a diverse patient demographic. The main clinic site is an inner-city clinic attached to the Women and Children's Hospital of Buffalo. In addition, there is a suburban satellite clinic and a suburban/rural satellite clinic. The Buffalo pediatric asthma service has 1160 patients in the age range proposed for the study and 315 new patients in this age range each year. Given these numbers, if 26% of caregivers have current MDD (as in our pilot study), then over a 4 year enrollment period the site will have 547 eligible participants. To enroll 98 participants, 18% of these will need to agree to participate.

Participant retention: We will use established methods for recruiting and retaining populations over long periods of time. Drs. [name] and [name] have used these methods throughout their multi-visit studies and obtained excellent retention statistics (95% completion of a 6 week study). [name] (PI) was an investigator on TMAP, a large multisite study using treatment algorithms for one year in patients with psychiatric illnesses in a similar fashion as the proposed study. In the MDD module of TMAP, retention was 100% at 3 months, 99.5% at 6 months, 83.2% at 9 months and 75.9% at 12 months. To maximize retention in the proposed study, multiple contact numbers (home, cell, work, family, friends), mailing addresses, and e-mail addresses will be obtained. Participants will be compensated appropriately for participation, transportation, time, and effort. Participants will have contact with research staff every 2-4 weeks either by phone or in person to keep them engaged in treatment. Participants are in the study for 52 weeks even if they miss some appointments, and we will collect as much data from each participant as possible. It is noteworthy that our data analytic procedures have robust methods of dealing with missing data. In addition, we propose enrolling 196 participants, rather than the 175 needed based on a power analysis, to allow for some early attrition.

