
Aim 3. Determine if improvement in depressive symptoms in the caregivers of children with asthma predicts improvement in asthma-related QOL in the caregiver and child. We will use the same approach outlined above under Aim 1 above but substituting the quality of life measure (PAQOL and PACQOL) in place of the asthma control measure.

Aim 4. Examine medication adherence and child anxiety/depression as possible mediators transmitting the effect of decreased caregiver depression on asthma control and unscheduled service utilization. The goal of Aim 4 is to validate the following relationships:

Caregiver HRSD (1) → medication adherence or child anxiety/depression (2) → child asthma outcomes (3)

The relationship between (1) and (3) is considered in Aim 1. For Aim 4, two sets of CLPM analyses, (1) → (2) and (2) → (3), will be done independently as described for Aim 1. The first set of analyses will determine if caregiver HRSD improvement (1) precedes child adherence (CAMPCS scores) and anxiety/depression

improvement (SCARED, CDI-Full Length scores) (2). Separate models will be fit for adherence and anxiety/depression. The second set of analyses will determine if child adherence and anxiety/depression improvement (2) precedes child asthma outcome improvement (3). Separate models will be fit relating adherence to each asthma outcome and relating anxiety/depression to each asthma outcome (6 models altogether). Similar analysis will be conducted replacing the HRSD with the caregiver scores on the QIDS-SR and STAI.

Missing Data: The analyses described here for the Primary Aim and Secondary Aim 2 will make use of data from all available subjects, even subjects with some missing data. Also, these models are unbiased if the missing data are missing at random (MAR).⁷⁶ However, in case the MAR assumption is not satisfied, we will investigate the effect of dropouts on the final results by introducing a variable into the models to indicate whether the patient dropped out or completed.⁷¹ If this dropout status variable is significant, then sensitivity analyses will be done to determine the possible effects of dropouts on the final results.^{72-74, 76, 77} The impact of missing data in the structural equation models will be assessed by using full information maximum likelihood.⁷⁸

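### Aim 2 admits only caregivers with two or more post-baseline HRSD scores, so the plan's all-subjects and missing-at-random statements do not hold for it as written

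*Combined protocol and SAP*

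**What the plan says.** Section 3.4, Aim 2, relates the number of emergency visits, hospitalizations or unscheduled appointments over the study to the caregiver's change in HRSD. The exposure is obtained by "computing a seasonally adjusted slope of change over time during the 52 week study", one value per caregiver. The analysis set follows: "All participants with two or more post-baseline HRSD measurements will be included in the analyses". For the outcome, incomplete follow-up is handled by a rate: "This number will be converted to events per month to adjust for subjects who do not complete 52 weeks".

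The Missing Data paragraph of section 3.4 reads: "The analyses described here for the Primary Aim and Secondary Aim 2 will make use of data from all available subjects", including those with some data missing. It adds that these models are unbiased under MAR. In case MAR fails, it proposes "introducing a variable into the models to indicate whether the patient dropped out or completed", followed by sensitivity analyses if that variable is significant.

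Section 3.3.c.ii (Participant retention) sets the enrolment margin: "we propose enrolling 196 participants, rather than the 175 needed based on a power analysis, to allow for some early attrition". It also keeps participants in the study for 52 weeks despite missed appointments. Section 3.3.d.iv supplements caregiver-reported utilization with hospital, physician and pharmacy records.

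Nothing in the plan says how caregivers below the two-score threshold are counted, described or analysed.

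**The concern.** The two paragraphs give different answers to the question of who is in the Aim 2 analysis. Having two post-baseline HRSD scores is something that happens after enrolment. It may be related both to the course of the caregiver's depression and to the child's asthma. If a family with several early emergency visits stops attending, the rule removes that caregiver and the child's events with them, even where the events are known from records.

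The study has a single group, so there is no randomization to break. What is at stake is the estimated association between HRSD change and utilization, and a report that could describe a selected set as all subjects and claim a MAR property that the method lacks.

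**Working it through.** **1. Who is included under each statement (section 3.4)**

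| HRSD data for the caregiver | Aim 2 rule | Missing Data paragraph |
|---|---|---|
| Baseline only, child's utilization known | out | in, on a plain reading |
| Baseline and one later score | out | in (a subject with some missing data) |
| Baseline and two or more later scores | in | in |

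The first two rows conflict.

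**2. Whether MAR carries over.** Let Y be the event count, X the HRSD slope, Z the covariates, and R = 1 if there are two or more post-baseline scores. The Aim 2 model estimates E[Y | X, Z, R = 1]. This equals E[Y | X, Z] if R is independent of Y given X and Z. MAR is a different condition: it lets missingness depend on anything observed, including observed events. R can therefore depend on observed Y with MAR satisfied, and the analysis restricted to R = 1 is then biased in general. A likelihood analysis using all observed data has the MAR property; a slope computed first and a regression on the selected set does not.

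**3. Whether the dropout indicator helps.** It is a term in the fitted model, and caregivers with R = 0 are not in that model. It compares completers only with those who dropped out after giving two scores. A non-significant result says nothing about the omitted group.

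**4. How many are affected.** Inputs: visits every 4 weeks, 13 after baseline (section 3.3.c), so the second post-baseline score is due at week 8; benchmark retention of 100% at 3 months and 99.5% at 6 months (section 3.3.c.ii); 196 to be enrolled and 175 needed.

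- Leaving before week 8 on the benchmark: 196 × (1 − 1.00) = 0 caregivers. Even by 6 months: 196 × (1 − 0.995) = 0.98, about 1.
- Enrolment margin: 196 − 175 = 21; 21/196 = 10.7%. This is a sample-size allowance. The plan does not say that these caregivers will have fewer than two scores.

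The benchmark comes from another study and describes leaving, not missed visits among those who stay, so the true share is unknown.

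**5. Power.** The plan's figure is reproduced first. Noncentral F test, u = 10, v = N − 11, noncentrality f² × N; alpha = 0.05 is assumed, because the Power paragraph gives none. At N = 175 and f² = 0.10 the noncentrality is 17.5 and power is 0.810; the detectable f² at 80% power is 0.098, against 0.10 stated. The match is to a joint test of all 10 predictors. With assumed shares removed from 196:

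| Removed | N | Power at f² = 0.10 |
|---|---|---|
| 0% | 196 | 0.863 |
| 5% | 186 | 0.840 |
| 10.7% | 175 | 0.810 |
| 12% | 172 | 0.801 |
| 15% | 167 | 0.785 |

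Power stays at about 0.80 or more until some 24 of 196 are removed. Power is not the main issue.

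**6. Why deleting the rule is not enough.** For visits at 0, 4, …, 4k weeks (t in years) and residual variance σ², a per-caregiver slope has variance σ²/Σ(t − t̄)². This gives 338σ² for k = 1, 84.5σ² for k = 2 and 0.743σ² for k = 13. Relative to full follow-up: 338/0.743 = 455 and 84.5/0.743 = 114. With baseline alone there is no slope at all.

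**The case against.** The strongest defence is that the two paragraphs can be read together: the available subjects are those whose slope can be computed. If the slope uses post-baseline scores only, two is the minimum; baseline depression is a separate covariate, and the threshold keeps a caregiver who missed 11 of 13 visits. This reading is possible, but the plan does not say whether baseline enters the slope. If it does, baseline plus one visit gives a slope and the rule still excludes that caregiver.

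The labels also leave room for doubt. The analyses are listed as Aims 1 to 4, while the Missing Data and Power paragraphs speak of a Primary Aim and Secondary Aims. Numbered in sequence, Secondary Aim 2 could be the quality-of-life aim. Aim 2 is the more natural match, because missing data in the structural equation models are treated separately, but the labels need reconciling.

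Three stronger readings are tempting, and the documents do not support them:

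- A reader might infer that the 21-person margin is the group the rule removes. Section 3.3.c.ii says only that it allows for early attrition, "rather than the 175 needed based on a power analysis, to allow for some early attrition". It is neither an estimate nor an upper bound for those below the threshold.
- A reader might infer that the omitted caregivers are early leavers. Participants remain in the study despite missed appointments, so a caregiver can fall below the threshold without leaving.
- A reader might infer that Aim 2 is therefore biased. Omitting subjects with a missing exposure causes bias only if omission depends on the outcome given the covariates, and the model already adjusts for site, baseline depressive symptoms and baseline asthma symptoms. Bias is possible and has not been shown.

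It is also true that a caregiver never seen again may supply little outcome data, and that one with few HRSD scores adds little information under any method.

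**Conclusion.** The inconsistency stands and should be corrected before analysis. As written, Aim 2 is a complete-case analysis on a derived exposure, and the plan cannot also describe it as using all subjects and as unbiased under MAR. The planned dropout check does not reach the omitted caregivers.

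The likely effect is small: about 0% lost through early leaving if the benchmark carries over, with an unknown addition from missed visits. Any harm would be a biased association between HRSD change and utilization, and a misdescribed analysis set, more than lost power. The conclusion assumes that Secondary Aim 2 means Aim 2; the power figures also assume alpha = 0.05.

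**What to change.** - Make the primary Aim 2 analysis a model of the integer event count with log(observed follow-up time) as offset, including every caregiver with any outcome follow-up.
- Take the HRSD trajectory from a joint or random-slope model, or from multiple imputation, fitted to all HRSD data including baseline, in place of separate per-caregiver slopes.
- Keep the two-score set as a sensitivity analysis.
- Report the number, baseline features and events of caregivers below the threshold, whatever the dropout indicator shows.
- State the same analysis set in the Aim 2 and Missing Data paragraphs, and use one set of aim labels throughout section 3.4.

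If the two-score rule is kept as primary, withdraw the all-subjects and MAR statements for Aim 2 and say that the analysis is complete-case on the exposure.

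The cost is a few sentences in section 3.4 and somewhat more modelling work, with no new data. The gain is limited by the fact that caregivers with little HRSD data add little information.
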